Study Endpoints	
Primary Study Endpoint H. pylori eradication rate (confirmed by ^{14}C UBT) on Days 28 to 34 after the last dose.
 
Secondary Study Endpoints
 
 1 The negative rate of ^{14}C UBT on Day 8 after the first dose; 2 The negative rate of ^{14}C UBT on Day 16 after the first dose; 3 Safety endpoints: Incidence of adverse events (AE) during the study, correlation with the investigational medicinal product and severity, laboratory tests, vital signs, ECG, physical examination, etc.; 4 Pharmacokinetic endpoints: Pharmacokinetic parameters of TNP-2198, rabeprazole, amoxicillin in each group of consecutive administrations.
Protocol No.	TNP-2198-PO-06
Sponsor	TenNor Therapeutics
Clinical Trial Notification No.	CXHL1800160/161
Study Facility	Phase I Drug Clinical Study Center of the First Hospital of Jilin University, Department of Gastroenterology of the First Hospital of Jilin University
Study Phase	Phase Ic/IIb

Investigational Products	
TNP-2198 capsules
 
 • Manufacturer: WuXi STA (Shanghai) Co., Ltd. (entrusted) • Strength: 100 mg • Storage Condition: Preserve in tightly closed containers, protected from light and stored at ambient temperature (10-30 °C) 
Rabeprazole Sodium Enteric-coated Tablets
 
 • Manufacturer: Eisai China Inc. • Drug Approval No.: GuoYaoZhunZi H20090090 • Strength: 20 mg • Storage Condition: Preserve in tightly closed containers, protected from light and stored below 25 °C 
Amoxicillin Capsules
 
 • Manufacturer: Zhuhai United Laboratories (Zhongshan) Co., Ltd. • Drug approval No.: GuoYaoZhunZi H44021351 • Strength: 0.5 g • Storage conditions: to be determined 												

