Study Design	
Study participant: 80 participants positive for H. pylori infection.
 
The purpose is to evaluate the efficacy, safety and tolerability, and pharmacokinetic characteristics of multiple-dose treatment with TNP-2198 capsules, rabeprazole sodium enteric-coated tablets and amoxicillin capsules, and TNP-2198 capsules and rabeprazole sodium enteric-coated tablets compared with continuous administration of rabeprazole sodium enteric-coated tablets and amoxicillin capsules.
 
In this study, a total of 4 test groups and 1 control group are set, 80 participants are planned to be enrolled and randomly assigned in a ratio of 2:2:1:1:2:
 
  
 Study grouping	Dosing regimen	Frequency of administration and course of treatment	Number of participants	
   
 Test group	 Group A: TNP-2198 capsules 400 mg, rabeprazole sodium enteric-coated tablets 20 mg, amoxicillin capsules 1 g Group B: TNP-2198 capsules 600 mg, rabeprazole sodium enteric-coated tablets 20 mg, amoxicillin capsules 1 g Group C: TNP-2198 capsules 600 mg, rabeprazole sodium enteric-coated tablets 20 mg Group D: TNP-2198 capsules 600 mg, rabeprazole sodium enteric-coated tablets 20 mg, amoxicillin capsules 1 g 	 BID × 14 days BID × 14 days TID × 14 days TID × 7 days 	 20 20 10 10 	
 
 Control group	Rabeprazole sodium enteric-coated tablets 20 mg, amoxicillin capsules 1 g	BID × 14 days	20	
  
 
Eligible participants will be admitted to the clinical study center 1 day before dosing (D-1).
 
Study procedures of Group A, Group B, Group C and Control Group (administration for 14 consecutive days):
	Study grouping	Dosing regimen	Frequency of administration and course of treatment	Number of participants	Test group	Group A: TNP-2198 capsules 400 mg, rabeprazole sodium enteric-coated tablets 20 mg, amoxicillin capsules 1 g Group B: TNP-2198 capsules 600 mg, rabeprazole sodium enteric-coated tablets 20 mg, amoxicillin capsules 1 g Group C: TNP-2198 capsules 600 mg, rabeprazole sodium enteric-coated tablets 20 mg Group D: TNP-2198 capsules 600 mg, rabeprazole sodium enteric-coated tablets 20 mg, amoxicillin capsules 1 g	BID × 14 days BID × 14 days TID × 14 days TID × 7 days	20 20 10 10	Control group	Rabeprazole sodium enteric-coated tablets 20 mg, amoxicillin capsules 1 g	BID × 14 days	20

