Dosing Regimen	
Group A, Group B and Control Group: Two doses per day, breakfast and dinner should be eaten within 30 minutes prior to dosing, and oral administration should be given after meals. All investigational products should be taken after meals for 14 consecutive days. On Day 15, participants will have breakfast within 30 minutes prior to dosing, and the last dose will be taken after completion of meals. Each participant will take 29 doses of investigational products.
 
Group C, Group D: Three doses per day, 8 hours apart. Group C is administered for 14 consecutive days, with the last dose on the morning of Day 15, and each participant receives 43 doses of investigational product; Group D is administered for 7 consecutive days, with the last dose on the morning of Day 8, and each participant receives 22 doses of investigational product.
 
The drug name, dose and course of treatment in each group are shown in the following table:
 
  
 Study grouping	Frequency of administration	Number of capsules/tablets per dose	Dosing course (days)	
 
 TNP-2198 capsules (100 mg/capsule)	Rabeprazole Sodium Enteric-coated Tablets (20 mg/tablet)	Amoxicillin Capsules (0.5 g/capsule)	
   
 Group A	BID	4	1	2	14	
 
 Group B	BID	6	1	2	14	
 
 Group C	TID	6	1	-	14	
 
 Group D	TID	6	1	2	7	
 
 Control group	BID	-	1	2	14	
  
	Study grouping	Frequency of administration	Number of capsules/tablets per dose			Dosing course (days)	TNP-2198 capsules (100 mg/capsule)	Rabeprazole Sodium Enteric-coated Tablets (20 mg/tablet)	Amoxicillin Capsules (0.5 g/capsule)	Group A	BID	4	1	2	14	Group B	BID	6	1	2	14	Group C	TID	6	1	-	14	Group D	TID	6	1	2	7	Control group	BID	-	1	2	14
Study grouping	Frequency of administration			Number of capsules/tablets per dose				Dosing course (days)																																

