Statistical Analysis	
Definition of Statistical Analysis Set:
 
 • Full Analysis Set (FAS): Refers to the participant of all randomized participants who have taken the investigational product at least once; • Modified Intent-to-Treat Analysis Set (mITT): Refers to all randomized participants who have ¹⁴C UBT performed on Day 28 to 34 after the last dose of the study; • Per Protocol Set (PP): Refers to participants without major protocol violation: participants who are randomized and receive more than 80% (inclusive) of the expected total amount of investigational product, and undergo ¹⁴C UBT on Day 28 to 34 after the last dose of the study; • Safety Analysis Set (SS): refers to the participant participant who entered the study and used the investigational product at least once; • Pharmacokinetic Concentration Analysis Set (PKCS): refers to all enrolled participants who have used the investigational product and have at least one observed PK concentration data; • Pharmacokinetic Parameter Analysis Set (PKPS): refers to all enrolled participants who have used the investigational product and have at least one observed PK parameter data. 
Demographic Analysis: Demographic analyses are based on the Full Analysis Set (FAS). Descriptive statistics will be performed for all demographics (age, gender, weight, height, BMI, ethnicity, etc.) and baseline characteristics, taking the last valid measurement data before the administration of the investigational product as the baseline.
 
Analysis of Helicobacter pylori eradication effect: The eradication effect will be analyzed descriptively by frequency (percentage) according to four ¹⁴C UBT results (negative or positive) at baseline, Day 8, Day 16, and Day 44 to 50 of follow-up in Group A, Group B, Group C and the Control Group, and three ¹⁴C UBT results (negative or positive) at baseline, Day 8, and Day 37 to 43 of follow-up in Group D, based on the full analysis set (FAS). And make inter-group comparison, which shall focus on comparison between the test group and the control group, supplemented by the comparison among the test groups. Inter-group comparison of percentages will adopt Fisher's exact test. H. pylori eradication rate is defined as the proportion of participants with negative ¹⁴C UBT results from Day 28 to Day 34 after the last dose of the study. At the same time, the H. pylori eradication rate of each group will be calculated in the mITT analysis set and the PP analysis set, and the sensitivity analysis will be performed. There are no clear statistical hypotheses in this study and all statistical tests are exploratory test with a two-sided 5% nominal significance level. The statistical analysis method and plan are detailed in the statistical analysis plan.

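### Does the 80% adherence rule for the per-protocol set need rewriting because it does not say how three drugs are counted?

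*Combined protocol and SAP*

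**What the plan says.** The Statistical Analysis section introduces the PP set with "Refers to participants without major protocol violation". After a colon it gives the conditions: the participant is randomized, must "receive more than 80% (inclusive) of the expected total amount of investigational product", and has a breath test 28 to 34 days after the final dose. It does not say whether the 80% is counted in capsules and tablets, in mg or in dosing occasions, or whether it applies to each drug.

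The Investigational Products section lists three drugs: TNP-2198 ("Strength: 100 mg"), rabeprazole ("Strength: 20 mg") and amoxicillin ("Strength: 0.5 g"). Regimens in the Study Design table combine two or three of them, for example "Group A: TNP-2198 capsules 400 mg, rabeprazole sodium enteric-coated tablets 20 mg, amoxicillin capsules 1 g".

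The Dosing Regimen table places every drug under the heading "Number of capsules/tablets per dose". For Groups A, B and Control the accompanying text says "Each participant will take 29 doses of investigational products"; the counts are 43 for Group C and 22 for Group D.

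Eradication is analysed on the FAS. Rates are also calculated in the mITT and PP sets, alongside a sensitivity analysis. The section states that there are no clear hypotheses and that every test is exploratory. It leaves further detail to the statistical analysis plan.

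**The concern.** All three drugs are investigational products, and the rule sets one threshold on one total. Read literally as a pooled sum, it lets full intake of one drug make up for missed intake of another. The number of units per dose differs by group (7, 9, 7, 9 and 3 in A, B, C, D and Control), so the room for such compensation differs too and is largest in the test groups.

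The PP rate is meant to show what happens when the regimen is taken as planned. A participant in A, B or D who took almost no amoxicillin would in effect have received the two-drug combination of Group C, in A at a lower TNP-2198 dose. If such people stayed in PP in the test groups while comparable people left it in Control, the PP rates would not be like for like. With 10 or 20 participants per group, one person can be visible in the result.

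**Working it through.** **Inputs.** Units per dose (TNP-2198 + rabeprazole + amoxicillin), from the Dosing Regimen table: A 4+1+2 = 7; B 6+1+2 = 9; C 6+1 = 7; D 6+1+2 = 9; Control 1+2 = 3. Strengths are 100 mg, 20 mg and 500 mg.

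**The plan's dose counts.** Doses per day × days + one final morning dose: 2×14+1 = 29 (A, B, Control); 3×14+1 = 43 (C); 3×7+1 = 22 (D). All three match the plan. These are dosing occasions. Counting each drug separately would give 3×29 = 87 in A and B and 2×29 = 58 in Control.

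**Reading 1: capsules and tablets pooled.** Find the fewest whole doses of one drug that still reach 80% of all units, with the other drugs taken in full.

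- Group B amoxicillin: total 9×29 = 261, threshold 0.8×261 = 208.8, other drugs 7×29 = 203. Then 203 + 2x ≥ 208.8 gives x = 3.
- Control amoxicillin: total 3×29 = 87, threshold 69.6, rabeprazole 29. Then 29 + 2x ≥ 69.6 gives x = 21.
- Rabeprazole is 1/7 (14.3%) or 1/9 (11.1%) of units in A to D, below the 20% allowance, so it can be zero there. Control: 58 + x ≥ 69.6 gives x = 12.

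**Reading 2: mg pooled.** Each participant may miss 20% of total mass.

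- Group B: total 29×(600+20+1000) = 46,980 mg, so 9,396 mg may be missed. That is at most 18 amoxicillin capsules, leaving 40 of 58 (20 doses).
- Control: total 29×(20+1000) = 29,580 mg, so 5,916 mg may be missed. That is at most 11 capsules, leaving 47 of 58 (24 whole doses).
- Rabeprazole is 1.2% to 3.2% of mass and can be zero in every group, Control included.
- TNP-2198 becomes the less protected drug: A 9/29, B 14/29, D 11/22.

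**Reading 3: dosing occasions, with the drugs of an occasion taken together.** 0.8×29 = 23.2, so 24; 0.8×43 = 34.4, so 35; 0.8×22 = 17.6, so 18.

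| Minimum amoxicillin doses to stay in PP | A | B | D | Control |
|---|---|---|---|---|
| Pooled units | 9/29 | 3/29 | 3/22 | 21/29 |
| Pooled mg | 21/29 | 20/29 | 15/22 | 24/29 |
| Dosing occasions | 24/29 | 24/29 | 18/22 | 24/29 |

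Applying 80% to each drug gives the same minimum numbers of whole doses as the last row.

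**Effect of one participant.** Removing one of n, with k eradicated, moves the rate by k/(n(n−1)) if that person failed and (n−k)/(n(n−1)) if eradicated. For illustration, assume n = 20 and k = 16: 16/380 = 4.2 points, or 4/380 = 1.1 points. The full 1/n (5 points at n = 20, 10 points at n = 10) arises only when that person is the group's sole failure or sole success.

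**The case for a change.** The strongest case for a change runs as follows. The PP text speaks of a total amount, not of doses, and the term cannot mean TNP-2198 alone because Control receives none, so a pooled sum is a natural literal reading. The occasion count helps only if an occasion requires every component; if any intake counted, a participant who took no amoxicillin could score 100%. The clause on major violations may be only a lead-in to the conditions after the colon, so it is not a sure safeguard. The trial is open-label, so an undefined rule leaves some room to choose PP membership after results are known. Under both pooled readings the amoxicillin bar is lower in the test groups than in Control. A remedy would take one phrase.

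Part of this stands: the unit is not stated, and the arithmetic under pooling is correct. But pooling is an inference. The large gap appears only when a 100 mg capsule counts the same as a 500 mg one, a measure few analysts would choose for a multi-drug regimen. The plan's own counting of doses as occasions points elsewhere. The scenario also needs someone to take one drug of a dose and leave another over most of the course. Dosing takes place during admission (D1 to D17, or D1 to D10 for Group D), people with known allergy to the products are excluded, and no section provides for stopping one drug while continuing the others. A new reaction during treatment could still lead to that, but such cases should be few.

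**Conclusion.** The gap is real but small, and analysts can be expected to fill it sensibly. Adherence in a combination regimen would ordinarily be computed per drug or per dosing occasion. Either way the threshold is 24 of 29 doses in A, B and Control, 35 of 43 in C and 18 of 22 in D, with no advantage to the test groups. The claim of an unequal bar depends on a pooled total that the plan does not state, and its size depends on the unit chosen.

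The consequence is also limited. The FAS carries the eradication analysis, PP rates are supplementary, the plan specifies no between-group test for the PP set in particular, and no confirmatory conclusion rests on it. One disputed participant moves a group's PP rate by at most 5 points (n = 20) or 10 points (n = 10), and usually by less.

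This conclusion assumes that the drugs of an occasion are normally taken together under inpatient dosing, and that the adherence calculation is not made by summing unlike capsules. Nothing in the documents contradicts either assumption. The missing detail does not make the plan's results or conclusions unsound, so no change is called for.

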Evaluation of Helicobacter Pylori Eradication	
Group A, Group B, Group C and Control Group: The ¹⁴C UBT are performed on participants under fasting conditions before breakfast at screening (D-14 to D-2), baseline (D-1), day 8 (D8), day 16 (D16) and day 44 to 50 (D44 to D50) to evaluate the effect of H. pylori eradication in each group. Group D: The ¹⁴C UBT will be performed on participants under fasting conditions before breakfast at screening (D-14 to D-2), baseline (D-1), Day 8 (D8) and Day 37 to 43 (D37 to D43) to evaluate the effect of H. pylori eradication.

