Screening period		Group A, Group B, Group C and Control Group				Follow-up period	End of Study
Baseline period		Hospitalization/Dosing period					
Day -14 to Day 2	Day -1 Randomization	Day 1 Daily oral administration of the investigational product for 14 consecutive days according to the dosing regimen	Day 14	Day 15 Oral administration of the last dose of the investigational product according to the dosing regimen	Day 17 Discharge may be allowed after completion of examinations and PK blood collection	Day 44 to Day 50 Return to the study center for ¹⁴ C UBT	
		Group A TNP-2198 Capsules 400 mg, Rabeprazole Sodium Enteric-coated Tablets 20 mg, Amoxicillin Capsules 1 g Twice daily					
		Group B TNP-2198 Capsules 600 mg, Rabeprazole Sodium Enteric-coated Tablets 20 mg, Amoxicillin Capsules 1 g Twice daily					
		Group C TNP-2198 Capsules 600 mg, Rabeprazole Sodium Enteric-coated Tablets 20 mg Three times daily					
		Control group Rabeprazole Sodium Enteric-coated Tablets 20 mg, Amoxicillin Capsules 1 g Twice daily					

Note: ¹⁴C UBT will also be performed for Group A, Group B, Group C and Control Group during the screening period, the baseline period, and on Day 8 and Day 16 during the hospitalization/dosing period.

Group D

Screening period		Hospitalization/Dosing period				Follow-up period	End of Study
Baseline period		Day 1.....	Day 7	Day 8	Day 10		
Day -14 to Day 2	Day -1 Randomization	Day 1..... Daily oral administration of the investigational product for 7 consecutive days according to the dosing regimen		Oral administration of the last dose of the investigational product according to the dosing regimen		Discharge may be allowed after completion of examinations and PK blood collection	
		Group D TNP-2198 Capsules 600 mg, Rabeprazole Sodium Enteric-coated Tablets 20 mg, Amoxicillin Capsules 1 g Three times daily					

Note: ¹⁴C UBT will also be performed for Group D during the screening period, the baseline period, and on Day 8 during the hospitalization/dosing period.

Schedule of Activities for Group A, Group B, Group C and Control Group

Study Procedures		Screening period	Baseline period	Hospitalization/Dosing period																	Follow-up period
		D-14~D-2	D-1	D1	D2	D3	D4	D5	D6	D7	D8	D9	D10	D11	D12	D13	D14	D15	D16	D17	D44~D50
Screening	Signing of ICF	X																			
	Demographics	X																			
	Medical and surgical history	X	X																		
	Concomitant medications	X	X	X	X	X	X	X	X	X	X	X	X	X	X	X	X	X	X	X	

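### Should the plan have named a dose-trend test across Control, Group A and Group B in addition to Fisher's exact test?

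*Combined protocol and SAP*

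**What the plan says.** In the Statistical Analysis section, under the analysis of *H. pylori* eradication effect, results are given as counts and percentages by group in the full analysis set. Groups are then compared, "which shall focus on comparison between the test group and the control group, supplemented by the comparison among the test groups". The test is named in one sentence: "Inter-group comparison of percentages will adopt Fisher's exact test". The status of the tests is stated too: "There are no clear statistical hypotheses in this study and all statistical tests are exploratory test with a two-sided 5% nominal significance level". Further detail is deferred: "The statistical analysis method and plan are detailed in the statistical analysis plan". That separate document is not reproduced in the file, so a trend test is not named here, which is different from being absent from the plan.

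The Study Design table assigns 20 participants each to A, B and Control, and 10 each to C and D. Under Dosing Regimen, A, B and Control have one rule: "Group A, Group B and Control Group: Two doses per day, breakfast and dinner should be eaten within 30 minutes prior to dosing". For all three the total is the same: "Each participant will take 29 doses of investigational products". Rabeprazole 20 mg and amoxicillin 1 g are common to them, and so are the breath-test days.

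**The concern.** Three randomized groups that differ only in the amount of one drug (0, 400, 600 mg) form a dose series. Pairwise Fisher tests treat the groups as unordered labels, so a steady rise spread over three groups can fail every comparison. With 12/20, 16/20 and 18/20 eradicated (Control/A/B), Fisher gives p = 0.30 for A against Control and p = 0.065 for B against Control, while an exact trend test with scores 0/400/600 gives p = 0.028. A trend test needs no extra participants, visits or data.

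There is also a case for fixing it early. Group percentages will be reported, a pattern will be visible, and a trend test chosen afterwards could be tuned through its scores. If the concern held, the trial would be giving up power and leaving room for a data-driven analysis.

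**Working it through.** **Inputs from the document.** Total 80, ratio 2:2:1:1:2 (parts sum to 8). Split: 80 × 2/8 = 20 for A, B and Control; 80 × 1/8 = 10 for C and D. This reproduces the table. There is no stated power or assumed eradication rate to reproduce. Significance level: two-sided 5%, nominal.

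**Assumption.** All eradication rates below are assumed, written Control/A/B.

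**Method.** All 21³ = 9,261 outcomes (c, a, b) for three groups of 20 were enumerated.

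- Trend statistic: T = 0·c + 400·a + 600·b. Given the total S = c + a + b, each outcome has weight C(20,c)·C(20,a)·C(20,b)/C(60,S), and the mean of T is S × 1000/3. The two-sided p-value is the total weight of outcomes at least as far from that mean as the observed one.
- Comparator: A or B significant against Control by Fisher's exact test.
- Power: the binomial probabilities of all outcomes with p ≤ 0.05, summed.

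**Power (%)**

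| Shape | Control/A/B | Fisher pair | Trend 0/400/600 | Difference |
|---|---|---|---|---|
| Rising | 60/80/90 | 52.9 | 59.9 | +7.0 |
| Rising | 70/90/95 | 50.7 | 60.4 | +9.7 |
| Rising | 65/80/95 | 60 | 61 | +1 |
| Level | 60/90/90 | 64.9 | 70.4 | +5.5 |
| 5-point fall at 600 mg | 60/90/85 | 57.1 | 55.1 | −2.0 |
| 10-point fall at 600 mg | 60/90/80 | 53 | 41 | −12 |
| Only 600 mg active | 60/60/90 | 50.4 | 40.9 | −9.5 |
| Only 600 mg active | 70/70/95 | 46 | 33 | −13 |
| Large effect | 30/80/90 | 99 | 99 | 0 |

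The sign of the difference depends on the shape of the response, and nothing in the document says which shape to expect.

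**Dependence on scores.** At 60/90/90%, scores 0/1/2 give 61.1%, below the Fisher pair's 64.9%. Scores 0/1/1, which simply set any TNP-2198 against none, give 71.6%, above the dose scores. At 60/90/85% the 0/1/1 contrast gives 60.4%, against 55.1% for the dose scores and 57.1% for the Fisher pair. At 60/80/90% it gives 49.8%, so there dose order does help.

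**What a significant trend would mean.** Take 12/20, 18/20, 17/20, where the 600 mg result is below the 400 mg result. S = 47 and T = 400 × 18 + 600 × 17 = 17,400. The conditional mean is 47 × 1000/3 = 15,666.7, so the distance is 1,733.3 and p = 0.033. With scores 0/1/2, p = 0.085; with 0/1/1, p = 0.022. The dose-score test is significant although the rates are not in dose order. The signal is drug against no drug, so a small p-value would not by itself establish a dose-ordered response.

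**Error rate.** Over common rates from 1% to 99%, the maximum chance of a false positive is 4.71% for the Fisher pair, 4.39% for the trend test alone, and 6.19% for the pair plus the trend test. Adding it costs 6.19 − 4.71 = 1.48 percentage points.

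**The case for a change.** The strongest reply is that the trend test would only supplement the Fisher comparisons, so its weak shapes do no harm to them. It respects its own 5% level (at most 4.39%), and naming it with its scores in advance closes off a choice that matters: 11/20, 15/20, 17/20 gives p = 0.039 with scores 0/400/600 and p = 0.054 with 0/1/2. The planned comparison of A with B cannot fill the gap, since its power at 60/80/90% is only about 7%.

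Much of this stands. Fisher's test does ignore dose order, the gains under a rising response are real, and a trend test devised after the results are seen would carry little weight. But the synopsis announces no trend test, so it leaves no scores undefined. A trend test would not separate 400 mg from 600 mg either. And with no hypothesis and no stated decision tied to significance, a few points of power for one more nominal p-value changes no conclusion that the plan is set up to draw. These arguments make the test a reasonable option; they do not make its omission a flaw.

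**Conclusion.** The concern does not hold. Fisher's exact test is valid for the planned comparisons, those comparisons match objectives worded by regimen, and the plan labels every test exploratory. A supplementary trend test is a trade-off: in the cases examined it gains about 1 to 10 points of power under rising or level response, loses about 2 to 13 points if response falls at 600 mg or only 600 mg is active, changes with the chosen scores, and raises the maximum three-group false-positive rate from 4.7% to 6.2%. The power figures rest on assumed eradication rates and on complete groups of 20. The separate statistical analysis plan could not be checked and may already name such a test; the conclusion is the same either way.

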Pharmacokinetics Sample Collection	
PK collection time points:
 
PK blood samples will be collected at the following time points.
 
1) Blood sampling time points in Group A, Group B and Control Group:
 
 • Day 1: within 30 Minutes Pre-dose, 0.5, 1, 1.5, 2, 2.5, 3, 3.5, 4, 5, 6, 7, 8, 9, 10, 11, 12 Hours Post-Dose (Prior to the Second Dose of the Day); • Days 3, 5, 7, 9, 11, 13, and 14: within 30 minutes prior to dosing; • Day 15: Within 30 Minutes Pre-dose, 0.5, 1, 1.5, 2, 2.5, 3, 3.5, 4, 5, 6, 7, 8, 9, 10, 11, 12, 24 Hours (Day 16) and 48 Hours (Day 17) Post-dose. 
2) Blood sampling time points in Group C:
 
 • Day 1: within 30 minutes before dosing, 0.5, 1, 1.5, 2, 2.5, 3, 3.5, 4, 5, 6, 7, 8 hours after dosing (prior to the second dose of the day); • Days 3, 5, 7, 9, 11, 13, 14: within 30 minutes prior to dosing;

	
 Day 15: Within 30 Minutes Pre-dose, 0.5, 1, 1.5, 2, 2.5, 3, 3.5, 4, 5, 6, 7, 8, 9, 10, 11, 12, 24 Hours (Day 16) and 48 Hours (Day 17) Post-dose. 
3) Blood sampling time points in Group D:
 
 Day 1: within 30 minutes before dosing, 0.5, 1, 1.5, 2, 2.5, 3, 3.5, 4, 5, 6, 7, 8 hours after dosing (prior to the second dose of the day); Days 3, 5, 7: within 30 minutes prior to dosing; Day 8: Within 30 Minutes Pre-dose, 0.5, 1, 1.5, 2, 2.5, 3, 3.5, 4, 5, 6, 7, 8, 9, 10, 11, 12, 24 Hours (Day 9) and 48 Hours (Day 10) Post-dose. 
PK blood sample processing method:
 
Whole blood is collected in vacutainers containing anticoagulant, 4 mL per tube, and plasma is obtained by centrifugation after completion of whole blood collection, and the plasma samples are divided into two aliquots and stored in a -80 °C refrigerator, one for pharmacokinetics analysis and the other as a backup. The process from sample collection to -80 °C refrigerator storage needs to be completed within 1 hour. Refer to the Laboratory Operation Manual for specific operation requirements.

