
	
Safety Analysis:
 
The analysis of safety and tolerability are mainly based on descriptive statistics. AEs, treatment-emergent adverse events (TEAEs), serious adverse events (SAEs), drug-related AEs and AEs leading to withdrawal from the study are summarized. The number, frequency and incidence of all adverse events will be tabulated and summarized by different groups, system organ class and preferred term. The number, frequency and incidence of adverse events of each grade will be tabulated according to CTCAE grade by different groups. The number, frequency and incidence of AEs in each group will be tabulated by system organ class and preferred term according to severity and relevancy to the investigational product. The number, frequency and incidence of common adverse events in each group will be tabulated and described by system organ class and preferred term. Laboratory test results that were normal before the test but abnormal after treatment are described by group. The mean, standard deviation, median, minimum and maximum values of vital signs (blood pressure, respiration, pulse and body temperature) and laboratory indicators before and after administration are calculated respectively by different groups. If necessary, paired t test or non-parametric test can be used for comparison before and after administration. SAE and suspected unexpected serious adverse reactions (SUSARs) are presented separately.
 
Pharmacokinetic Analysis:
 
Non-compartmental pharmacokinetic parameters are estimated and analyzed for plasma concentration data using Phoenix WinNolin software, PK concentration data are analyzed using PKCS, and main pharmacokinetic parameters are calculated using PKPS data. Participants with serious deviations from the study protocol should be excluded from the pharmacokinetic analysis. The results of the analysis of the main pharmacokinetic parameters are summarized by groups using sample size, arithmetic mean, standard deviation, coefficient of variation, median, minimum, maximum and geometric mean and geometric coefficient of variation. Main pharmacokinetic parameters include: PK parameters of the first dose, such as T_{max}, C_{max}, $t_{1/2}$, $AUC_{0-\infty}$, AUC_{0-tau}, Vd/F, CL/F, etc.; PK parameters of the last dose, including $T_{max,ss}$, $C_{max,ss}$, $C_{min,ss}$, $C_{avg,ss}$, $t_{1/2,ss}$, $AUC_{0-last,ss}$, $AUC_{0-tau,ss}$, $AUC_{0-\infty,ss}$, V/F_{ss}, CL/F_{ss}, Rac, DF, etc.

--	--

Study Design

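### The one inferential method named for safety is an optional within-group before/after test, which does not use the randomised Control and so cannot separate regimen effects from non-drug change

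*Combined protocol and SAP*

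**What the plan says.** Under Study Design, the synopsis states the purpose as evaluating efficacy, safety, tolerability and pharmacokinetics of the test regimens "compared with continuous administration of rabeprazole sodium enteric-coated tablets and amoxicillin capsules". The allocation is given as "80 participants are planned to be enrolled and randomly assigned in a ratio of 2:2:1:1:2", with 20 participants each in A, B and Control and 10 each in C and D.

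Under Statistical Analysis, the Safety Analysis paragraph opens: "The analysis of safety and tolerability are mainly based on descriptive statistics". Adverse events and normal-to-abnormal laboratory results are tabulated by group. Summary statistics for vital signs and "laboratory indicators before and after administration are calculated respectively by different groups". The only test follows: "If necessary, paired t test or non-parametric test can be used for comparison before and after administration". No difference, interval or test against Control is named for any safety variable.

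Fisher's exact test and the emphasis on test versus control appear only in the eradication paragraph. That paragraph also says that "all statistical tests are exploratory test with a two-sided 5% nominal significance level" and refers to a statistical analysis plan for detail. The Demographic Analysis paragraph defines baseline by "taking the last valid measurement data before the administration of the investigational product as the baseline".

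**The concern.** A before/after test in one arm asks whether the mean changed, not whether the regimen changed it. Non-drug change is plausible here. Groups A, B, C and Control stay in the unit from D1 to D17 and Group D from D1 to D10. Under Pharmacokinetics Sample Collection, "Whole blood is collected in vacutainers containing anticoagulant, 4 mL per tube", at many time points, and safety-laboratory blood comes on top. Any resulting shift is credited to the arm in which it is tested, Control included.

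Rejection also depends on arm size. The two arms of 10 are the TID arms, so for an equal shift they are flagged less often than A and B. Someone comparing p-values across arms, or against Control, could draw a wrong safety conclusion in either direction. The randomised group that would answer the question is already in the trial.

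**Working it through.** **Inputs from the document.** Group sizes: 80 × (2, 2, 1, 1, 2)/8 = 20, 20, 10, 10, 20, which matches the Study Design table. Significance level: two-sided 5%, nominal. The synopsis gives no power, effect size or SD for any safety variable.

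**PK blood, counted from the sampling schedule at 4 mL per tube (first day + troughs + last-dose profile).**

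- A, B, Control: 17 + 7 + 19 = 43 tubes, 172 mL
- C: 13 + 7 + 19 = 39 tubes, 156 mL
- D: 13 + 3 + 19 = 35 tubes, 140 mL

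The volume of safety-laboratory blood is not stated.

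**Assumption.** A common non-drug shift d (mean change divided by SD of change) in every arm, and no drug effect. The document gives no value, so a range is shown.

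**Rejection probability of the paired t test.** Noncentral t with n − 1 degrees of freedom and noncentrality d√n, two-sided 0.05:

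| d | n = 20 | n = 10 |
|---|---|---|
| 0 | 5% | 5% |
| 0.2 | 13.6% | 8.8% |
| 0.3 | 24.7% | 13.6% |
| 0.5 | 56.5% | 29.3% |
| 0.8 | 92.4% | 61.6% |

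The n = 20 figure at d = 0.5 is 56.45% before rounding. The Wilcoxon signed-rank test behaves alike: by simulation at d = 0.5, 54% and 28%.

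The smallest observed mean change that reaches p < 0.05 is t(0.975, n − 1)/√n: 2.093/√20 = 0.47 SD for n = 20 and 2.262/√10 = 0.72 SD for n = 10.

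**Reading the arms side by side by eye (independent arms, d = 0.5).**

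- Test arm significant, Control not, 20 v 20: 0.565 × (1 − 0.565) = 25%
- Test arm significant, Control not, 10 v 20: 0.293 × (1 − 0.565) = 13%
- Control significant, test arm of 10 not: 0.565 × (1 − 0.293) = 40%

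At d = 0.8 the first figure falls to 0.924 × 0.076 = 7%, because both arms are then nearly always significant.

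**Direct comparison with Control.** With the same shift in both arms and no drug effect, a two-sample t test on change rejects in 4.8% to 5.1% of simulated trials (100,000 runs per setting; d = 0, 0.5, 0.8), for 20 v 20 and 10 v 20.

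The 95% CI half-width is t(0.975, n₁ + n₂ − 2) × √(1/n₁ + 1/n₂), in SDs of change:

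- 20 v 20: 2.024 × 0.316 = 0.64 SD
- 10 v 20: 2.048 × 0.387 = 0.79 SD

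Power for a true 0.8 SD effect is 69% and 51%, so the estimate with its interval is more useful than a p-value.

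**The case against.** The strongest reply is that the safety analysis is mainly descriptive, the test is optional and all tests are exploratory. Nothing says that a significant before/after change will be read as a drug effect or used to rank arms. That stands. A reader might infer that the plan will call confinement and blood-draw effects drug effects. The text does not support this; it supports only that the p-values can mislead. The condition for using the test has no stated criterion, however, so the choice could be made after seeing the data.

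A reader might also infer that the safety analysis ignores Control. It does not. The tables are by group, and a shared drift would show in Control too. What they lack is a difference and its precision, and comparing p-values by eye is a poor substitute.

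A third tempting reading is that C and D would look safer purely because they are small. The size effect is real for an equal shift. But Group D also has a shorter stay and fewer draws, so a lower rate there could reflect a smaller shift. Group C, with the same stay as A and B and 39 draws against 43, is the cleaner illustration.

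Finally, the text available is a synopsis that refers to a statistical analysis plan for detail. The point is therefore limited to what the synopsis names.

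**Conclusion.** The concern holds in a limited form. The one inferential method named for safety leaves out the randomised Control, so it cannot separate regimen effects from non-drug change and does not serve the stated comparative purpose. For a shared shift of 0.3 to 0.5 SD and no drug effect, it is significant in 25% to 56% of arms of 20 against 14% to 29% of arms of 10. A comparison with Control stays at about 5%.

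These figures rest on an assumed shift that is equal across arms. With no shift, both arm sizes reject at 5%. This should be corrected, but it does not invalidate the descriptive safety tables.

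**What to change.** Replace the sentence on the paired test with:

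> For continuous laboratory values and vital signs, the baseline-adjusted difference in change from baseline, each test group minus Control, will be shown with its 95% CI at common study days (for Group D, up to and including the D8 pre-dose visit; later Group D visits are descriptive only). Any within-group before/after p-values will be labelled descriptive and not read as drug effects.

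D8 is the natural last common day for Group D. Both schedules of activities take laboratory tests before the first dose that day, when Group D has had 7 × 3 = 21 of its 22 doses. PK tubes drawn through D7 are 13 + 3 = 16 (64 mL) in D and 17 + 3 = 20 (80 mL) in Control. Setting D10 in Group D against D17 in Control would instead bring in seven extra days of confinement.

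State also that the contrast isolates TNP-2198 only for A and B. Group C is TID without amoxicillin, and Group D differs from Control in frequency and duration, so for these two it compares whole regimens. Keep all scheduled vital-sign times in the tables.

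The cost is SAP wording and one table shell, with no new data. Intervals for C and D will be wide (about ±0.79 SD before any gain from baseline adjustment), which reflects what 10 v 20 can show.
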